13. FACILITIES

Selection of specific study vendors is pending.

14. USE OF INFORMATION AND PUBLICATION POLICY

14.1. Use of Information

All information concerning Cannabidiol Oral Solution and Insys Development Company's operations, such as Insys' patent applications, formulas, manufacturing processes, basic scientific data, or formulation information, supplied by Insys Development Company and not previously published, is considered confidential information.

This confidential information shall remain the sole property of Insys Development Company, shall not be disclosed to others without the written consent of Insys Development Company, and shall not be used except in the performance of this study.

The investigator will maintain a confidential patient identification code list of all patients enrolled in the study (by name and patient number). This list will be maintained at the site, and will not be retrieved by Insys.

14.2. Publication Policy

Insys Development Company, Inc. will retain ownership of all data. All proposed publications based on this study will be patient to the sponsor's approval requirements.

Document Date: 9 July 2018

Page 8 of 39
ST-AD-008 version 04

Downloaded by PPD on 10/12/2022

Statistical Analysis Plan

Sponsor Name: Insys Development Company, Inc.
Sponsor Protocol ID: INS011-16-085

Covance Study ID: 000000163564

1. Source Documents

The Statistical Analysis Plan (SAP) was written based on the following documentation:

Document	Date	Version
Protocol Amendment 1	18 May 2018	3.0
eCRF	31 May 2018	1.0

2. Protocol Details

2.1 Study Objectives

2.1.1 Primary Objective

The primary objective of this study is to assess the efficacy of Cannabidiol Oral Solution on hyperphagia-related behavior in patients with Prader-Willi Syndrome (PWS) as measured by the total score of the Hyperphagia Questionnaire for Clinical Trials (HQ-CT).

2.1.2 Secondary Objectives

The secondary objectives of this study are:

- To assess the efficacy of Cannabidiol Oral Solution on the change in total body weight in patients with PWS.
- To assess the responder rate (responder is defined as a 6-point decrease on the HQ-CT from Baseline to End of Study).
- To assess the efficacy of Cannabidiol Oral Solution by measuring Patient Global Impression of Change (PGI-C).
- To assess the safety and tolerability of Cannabidiol Oral Solution in patients with PWS.
- To assess the efficacy of Cannabidiol Oral Solution on eating behavior in patients with PWS as measured by the Three Factor Eating Questionnaire -18-item version (TFEQ-R18).
- To assess the impact on Quality of Life in patients with PWS as measured by the PROMIS[®] Life Satisfaction and Positive Affect short-form questionnaires.
- To assess the impact on physical activity in patients with PWS as measured by the PROMIS[®] Physical Activity and Fatigue questionnaires.

Statistical Analysis Plan

Sponsor Name: Insys Development Company, Inc.
Sponsor Protocol ID: INS011-16-085

Covance Study ID: 000000163564

2.1.3 Exploratory Objective

The exploratory objective of this study is to assess the efficacy of Cannabidiol Oral Solution on body composition and bone mineral density, as measured by dual-energy X-ray absorptiometry (DEXA).

2.2 Overall Study Design

This study is a double-blind, randomized, placebo-controlled, Phase 2 clinical trial in patients aged 8 to 17 years inclusive, with a genetically confirmed diagnosis of PWS.

Approximately 66 patients will be randomized in a 1:1 ratio to receive either:

- Cannabidiol Oral Solution (40 mg/kg/day) divided into twice daily doses with standard meal
- Matching placebo, divided into twice daily doses with standard meal

Randomization will be stratified according to use of growth hormone (Yes, No).

Patients will participate in the study for approximately 19 weeks. The study will consist of the following 6 periods:

- Screening Period (2 weeks)
- Placebo Lead-in Period (2 weeks)
- Titration Period (1 week)
- Maintenance Period (12 weeks)
- Taper Period (1 week)
- Follow-up Period (1 week)

Eligible patients will be assigned to a 2-week single-blind placebo lead-in period after which they will be randomly assigned to receive double-blind treatment with either Cannabidiol Oral Solution (40 mg/kg/day) or matching placebo (a 1-week Titration Period followed by a 12-week Maintenance Period). During the Titration Period Cannabidiol Oral Solution will be titrated as follows: Days 1-3: 20 mg/kg/day, Days 4-6: 30 mg/kg/day, Day 7: 40 mg/kg/day.

During the Maintenance Period, patients may have their dose of blinded study medication adjusted down to 30 mg/kg/day at the discretion of the investigator or qualified designee based on the patient's tolerability.

After completion of the study, patients will be offered an opportunity to enroll into an open-label, long-term safety study. Patients who do not elect to enroll in the long-term safety study will be titrated off study drug over 7 days and a final safety follow-up phone call will be placed 2 weeks after study completion for patients who do not elect to continue in the long-term safety study.

[figure not shown]
Statistical Analysis Plan

Sponsor Name: Insys Development Company, Inc.
Sponsor Protocol ID: INS011-16-085

Covance Study ID: 000000163564

The study design is depicted in [Figure 1](#).

Figure 1: Study Design Schematic

All screening, efficacy and safety evaluations will be performed according to the schedule of assessments summarized in [Appendix A](#).

2.3 Sample Size and Power

A total of 30 patients per treatment group will provide at least 85% power with an alpha of 0.05, to detect a difference in the change in HQ-CT from Baseline to Week 13 of 5 points with a standard deviation of 6. Assuming a 20% drop out rate, approximately 66 patients (33 patients per arm) will be randomized to achieve 60 (30 patients per arm) completers.

3. Efficacy and Safety Endpoints

3.1 Primary Efficacy Endpoint(s)

The primary efficacy endpoint for this study is change in the total score of the HQ-CT from Baseline (defined as the score after the Placebo lead-in period) through Study Completion (Week 13/Early Withdrawal). The HQ-CT is a 9-item questionnaire and the response for each item ranges from 0 (for responses such as "Not at all" or "Never") to 4 (for responses such as "Several times"). The total HQ-CT score is then obtained by summing the responses to each item, yielding a total HQ-CT score that can range from 0 to 36 (Fehnel, et al., 2015).

Statistical Analysis Plan

Sponsor Name: Insys Development Company, Inc.
Sponsor Protocol ID: INS011-16-085

Covance Study ID: 000000163564

3.2 Secondary Efficacy Endpoints

The secondary efficacy endpoints in this study are:

- Change in total body-weight from Baseline through Study Completion/Early Withdrawal.
- Responder rate (responder is defined as 6-point decrease on the HQ-CT from Baseline through Study Completion).
- Patient Global Impression of Change and Severity.
- Change in the TFEQ-R18 from Baseline through Study Completion/Early Withdrawal. The TFEQ-R18 yields scores for 3 subscales: cognitive restraint, uncontrolled eating and emotional eating (Karlsson et al., 2000). The scores for each subscale will be analyzed separately.
- Change in Quality of Life (PROMIS[®] Life Satisfaction and Positive Affect questionnaires) from Baseline through Study Completion/Early Withdrawal.
- Change in physical activity (PROMIS[®] Physical Activity and Fatigue questionnaires) from Baseline through Study Completion/Early Withdrawal.

Methods for scoring the TFEQ-R18 and the PROMIS[®] questionnaires are provided in [Appendix B](#) and [Appendix C](#) respectively.

3.3 Exploratory Efficacy Endpoint

The exploratory efficacy endpoint is change in body composition from Baseline to Study Completion/Early Withdrawal as measured by DEXA.

3.4 Safety Endpoints

The safety endpoints of this study are:

- Treatment-emergent adverse events (TEAEs)
- Clinical laboratory assessments
- Vital signs (blood pressure, pulse rate, respiration rate and temperature)
- 12-lead ECGs
- Physical examination assessments
- Pregnancy screens
- Urine drug screen (including THC)
- Medical history
- Prior and concomitant medications.

4. Pharmacokinetic Endpoints

The pharmacokinetic (PK) endpoints of this study are trough concentrations (C_{trough}) of cannabidiol (CBD) and metabolite 7-OH-CBD which will be used to assess the exposure-response relationship.

Statistical Analysis Plan

Sponsor Name: Insys Development Company, Inc.
Sponsor Protocol ID: INS011-16-085

Covance Study ID: 000000163564

5. Analysis Populations

Unless otherwise stated, all efficacy analyses will be performed on the Intent-to-treat (ITT) population. A supportive analysis of the primary endpoint will also be performed on the Per-protocol (PP) population. All safety analyses will be performed on the safety population. Analyses of the DEXA endpoints will be performed on the DEXA population. The analysis of the PK endpoints will be performed on the PK population.

5.1 Intent-to-treat Population

The ITT population will consist of all randomized patients. ITT patients are analyzed according to their randomized treatment.

5.2 Safety Population

The Safety population includes all randomized patients treated with at least one dose of the study drug during the double-blind treatment period. Safety patients are analyzed according to their actual treatment received.

5.3 Per Protocol Population

The PP population will consist of all patients in the ITT population who do not have any important protocol deviations leading to exclusion from the PP population.

Protocol deviations are defined as any change, divergence, or departure from the study design or procedures defined in the study protocol. Important protocol deviations are a subset of protocol deviations and may significantly impact the correctness, accuracy, and/or reliability of the study data or that may significantly affect a subject's rights, safety, or well-being. Section 5.3.1 details the deviations.

All important and non-important protocol deviations are defined in a protocol deviations list which includes details about escalation requirements and whether they are detected via monitoring or programming.

5.3.1 Important Protocol Deviations Leading to Exclusion from the PP Population Analysis

Only the important protocol deviations considered as having a major effect on the collection or interpretation of the efficacy data will lead to complete exclusion of patients from the PP population.

For the purposes of this study, the following criteria have been identified as important protocol deviations leading to exclusion from the PP population as it is considered that the occurrences of any of these criteria might have an important influence on the primary efficacy endpoint:

Statistical Analysis Plan

Sponsor Name: Insys Development Company, Inc.
Sponsor Protocol ID: INS011-16-085

Covance Study ID: 000000163564

Table 1: Important Protocol Deviations Leading to Exclusion from the PP Population

Type	Important Protocol Deviation Leading to Exclusion from the PP Population	Method of Identification
Non-compliance during the double-blind treatment phase	Patients who had low study drug compliance (e.g. repeated occurrence of compliance < 90%)	Programmable check based on the exposure and drug accountability data.
Errors in treatment allocation	Patients who receive the wrong treatment at 1 or more study visit due to packaging or dispensing errors	Programmatic check based on the unblinded IWRS database after the study is unblinded. The check will be performed by comparing the kit number assigned by IWRS to the patient at a particular visit against the kit number actually used.
CTMS	Covance Clinical will provide the list of protocol deviations based on the clinical monitoring.	Manual review: The list will be reviewed and the important protocol deviations that will lead to exclusion from the PP population will be identified.

As defined in [Table 1](#), the majority of the important protocol deviations leading to exclusion from the PP population will be determined programmatically from the data. Those criteria which require clinical or medical monitoring interpretation will be reviewed prior to database lock.

All important protocol deviations leading to exclusion from the PP population occurring during the study will be reviewed and approved by Insys prior to database lock and unblinding. Should additional important protocol deviations leading to exclusion from the PP population, not anticipated at the time of preparing this SAP, be identified during the study (and prior to unblinding) they will be documented in a SAP amendment and included in all relevant protocol deviation reviews and approvals.

5.4 DEXA Population

The DEXA population is a pre-defined subpopulation of approximately 20 patients from the ITT population for whom changes in body composition (total fat, lean body mass and bone mineral content) are assessed via DEXA scans.

Statistical Analysis Plan

Sponsor Name: Insys Development Company, Inc.
Sponsor Protocol ID: INS011-16-085

Covance Study ID: 000000163564

5.5 PK Population

The PK population will include patients who receive at least one dose of CBD and who have at least one usable CBD plasma concentration measurement.

6. DATA Handling

6.1 Time points and Visit Windows

Day 1 is defined as the date of first dose of double blind treatment. Relative days after Day 1 are calculated as (assessment date – Day 1 date) + 1. Relative days prior to Day 1 are calculated as (assessment date – Day 1 date). The day prior to Day 1 is Day -1.

All data will be analyzed using nominal study visits as defined in the Study Schedule (see [Appendix A](#)). No visit windows will be applied for summary and analysis.

For all populations, multiple visits within the same protocol-defined scheduled window (see [Appendix A](#)) will be dealt with as follows:

- If multiple scheduled visits occur within a single protocol-defined visit window then the visit closest to the target day of the visit window will be used in the analysis. In cases where the measurements are equal distances from the target day, the later visit will be used in the analysis.

6.2 Handling of Dropouts, Missing Data, and Outliers

Missing data will not be imputed for the safety analyses. Safety summaries will be based on observed data only.

For adverse events (AEs) with missing or partial start date:

- If the partial onset date does not indicate whether the AE started prior to or after the end of the treatment-emergent period (last dose of double-blind treatment plus 14 days), the AE will be classified as treatment-emergent.
- If the AE onset date is partial or missing, the AE end date will be considered. If the AE end date is partial and the partial end date does not indicate that the AE ended prior to the start of double-blind treatment, the AE will be classified as treatment-emergent.

In the event that a partial date for concomitant medication is available, this partial information will be used as follows:

- If the partial start date does not indicate whether the medication started prior to or after double-blind treatment, the medication will be classified as both prior and concomitant.

Statistical Analysis Plan

Sponsor Name: Insys Development Company, Inc.

Sponsor Protocol ID: INS011-16-085

Covance Study ID: 000000163564

- If the partial end date does not indicate that the medication ended prior to the start of double-blind treatment, the medication will be classified as both prior and concomitant.

The imputations for AEs and medications are for categorization purposes only and will not be used in listings.

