8.6.4.1. Adverse Events

The Medical Dictionary for Regulatory Activities (MedDRA, version 20.0) will be used to classify all AEs. Adverse event summaries will include only treatment-emergent AEs (TEAEs). Treatment-emergent adverse events (TEAEs) are defined as AEs that first occurred or worsened during the indicated treatment period.

The number and percentage of patients with TEAEs will be summarized by system organ class (SOC) and preferred term (PT). Summaries of AEs by severity and relationship to the study treatment will also be provided. Serious adverse events (SAEs) and AEs resulting in discontinuation will be summarized separately in a similar manner. Patient listings of AEs and SAEs will be produced.

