7.4.3 Previous and Concomitant Medications

Medications received prior to or concomitantly with treatment will be coded by Covance using the WHODrug Dictionary [Version March 2018 (or a later version if updated during the study)] Anatomical Therapeutic Chemical (ATC) Classification codes.

Prior medications and concomitant medications are defined as follows:

Prior medications are those taken prior to the first dose date of double-blind IMP treatment.

Concomitant medications are those with a start date on or after the first dose date of double-blind IMP treatment, or those with a start date before the first dose date of double-blind IMP treatment and a stop date on or after the first dose date of double blind treatment or ongoing at the end of the study.

If a medication cannot be classified as "prior" or "concomitant" after applying imputation rules for missing/incomplete dates, it will be classified as concomitant.

Prior medications and concomitant medications will be listed together and summarized separately for the ITT population.

The number and percentage of patients using each medication will be displayed together with the number and percentage of patients using at least one medication within each therapeutic class (ATC-Level 2), chemical subgroup (ATC-Level 4), and generic term.

COVANCE INC. CONFIDENTIAL

Document Date: 9 July 2018

Page 20 of 39
ST-AD-008 version 04

Downloaded by PPD on 10/12/2022

Statistical Analysis Plan

Sponsor Name: Insys Development Company, Inc.
Sponsor Protocol ID: INS011-16-085

Covance Study ID: 000000163564

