7.7.2 Adverse Events

All AEs recorded on the eCRF will be coded using the MedDRA dictionary [Version 21.0 (or a later version if updated during the study)] and classified as treatment – emergent AEs (TEAEs) as follows:

- TEAEs are events with start date on or after the date of first dose of double-blind IMP and up to 14 days after the last dose of double blind IMP or events with start date prior to the date of first dose of double-blind IMP whose severity worsens on or after the date of first dose of double-blind IMP.

All AE data will be listed by treatment group. Treatment-emergence status will be flagged in the listing. In addition, corresponding listings of treatment-emergent serious AEs (TESAEs), AEs leading to permanent discontinuation of IMP and AEs resulting in death will be produced.

Summary tables of TEAEs by treatment group and overall will be produced for the Safety population. No statistical comparisons of AEs between treatment groups will be performed.

The severity of all AEs is recorded as mild, moderate, or severe. If severity is missing for a TEAE, it will be considered severe.

The relationship between an AE and IMP treatment is assessed as definite, probable, possible, unlikely or not related. A treatment-related AE is an AE considered by the investigator as definitely, possibly, or probably related to IMP treatment or with unknown/missing relationship to IMP treatment.

An overview table will summarize the number and percentage of patients with at least one of the following TEAEs, where patients with more than one TEAE in a particular category are counted only once in that category:

- any TEAE;
- TEAE by severity (mild, moderate, severe);
- treatment-related TEAE;
- severe treatment-related TEAE;

COVANCE INC. CONFIDENTIAL

Document Date: 9 July 2018

Page 26 of 39
ST-AD-008 version 04

Downloaded by PPD on 10/12/2022

Statistical Analysis Plan

Sponsor Name: Insys Development Company, Inc.

Sponsor Protocol ID: INS011-16-085

Covance Study ID: 000000163564

- TESAE;
- TESAE by severity;
- treatment-related TESAE;
- TEAE leading to study drug discontinuation.

The overview table will be repeated to summarize the number of TEAEs (displaying the number and percentage of observed events).

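### In two narrow cases the partial-date rules in SAP 6.2 contradict the SAP's own definitions of treatment-emergent AE and prior medication

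*SAP*

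**What the plan says.** SAP 6.2 has two rules for AEs with an incomplete start date.

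- AE rule 1 covers an onset that cannot be placed relative to the end of the treatment-emergent window (last double-blind dose plus 14 days): "If the partial onset date does not indicate whether the AE started prior to or after the end of the treatment-emergent period", the event is treatment-emergent.
- AE rule 2 opens with "If the AE onset date is partial or missing, the AE end date will be considered". For an end date that is itself incomplete, a further condition and its result follow: "the partial end date does not indicate that the AE ended prior to the start of double-blind treatment, the AE will be classified as treatment-emergent".

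It also has two rules for medications.

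- Medication rule 1 covers a partial start date that leaves the start undetermined relative to double-blind treatment. The drug is then both prior and concomitant.
- Medication rule 2 covers the end date: "If the partial end date does not indicate that the medication ended prior to the start of double-blind treatment", the drug is again both. It sets no condition on the start date.

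The definitions stand elsewhere. The first limb in SAP 7.7.2 is "TEAEs are events with start date on or after the date of first dose of double-blind IMP", with a limit of 14 days beyond the last dose. The second limb is "events with start date prior to the date of first dose of double-blind IMP whose severity worsens on or after the date of first dose". Protocol 8.6.4.1 agrees: "AEs that first occurred or worsened during the indicated treatment period". SAP 7.4.3: "Prior medications are those taken prior to the first dose date of double-blind IMP treatment"; a drug whose start date is on or after first double-blind dose is concomitant.

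**The concern.** Rules for incomplete dates should settle what the recorded part of a date leaves open. They should not override what it already shows. AE rule 1 tests the onset only against the end of the window, and AE rule 2 looks only at the end date. Neither compares a partial onset with first double-blind dose. Medication rule 2 likewise ignores a start date that may be fully known.

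The AE case can arise. Dosing begins with the two-week placebo lead-in (Protocol Table 1), AEs are reviewed during it, and SAP 7.7.2 plans a separate table of run-in AEs. A lead-in event with partial dates could therefore appear both there and among the TEAEs. Prior and concomitant drugs are summarised separately (SAP 7.4.3), so the medication error also reaches a reported table. What is at stake is the accuracy of those descriptive counts and the SAP's agreement with itself on a safety endpoint.

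**Working it through.** The plan states no figure to reproduce. The check applies the four rules of SAP 6.2 literally to test dates and compares each result with SAP 7.7.2 or 7.4.3.

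Illustrative assumptions: first double-blind dose (Day 1) 10 Aug 2018; last dose 90 days later, 8 Nov 2018; window closes 8 Nov + 14 days = 22 Nov 2018. The lead-in then starts 10 Aug − 14 days = 27 Jul 2018.

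**Adverse events**

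| Onset | End | SAP 6.2 | SAP 7.7.2 |
|---|---|---|---|
| Jul 2018 | Aug or Sep 2018 | Treatment-emergent (rule 2) | Known pre-dose: only if worsened. **Conflict** |
| Jul 2018 | 20 Aug 2018 (full) | No rule applies | Known pre-dose: only if worsened. No conflict |
| Jul 2018 | Missing | No rule applies | Known pre-dose: only if worsened. No conflict |
| Jul 2018 | Jul 2018 | Not caught: ended before Day 1 | Not treatment-emergent. No conflict |
| Aug 2018 | Sep 2018 | Treatment-emergent (rule 2) | Undetermined; cautious assignment is acceptable |
| Dec 2018 | Dec 2018 | Treatment-emergent (rule 2) | Known to start after 22 Nov. **Conflict** |

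In the first row, rule 1 is silent because July is plainly before 22 Nov. Rule 2 is triggered because the onset is partial, and it classifies on the end date alone. In the last row, rule 1 is silent because December is plainly after 22 Nov, and rule 2 again decides on the end date alone.

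**Medications**

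| Start | End | SAP 6.2 | SAP 7.4.3 |
|---|---|---|---|
| 1 Sep 2018 (full) | Sep 2018 | Prior and concomitant (rule 2) | Concomitant only. **Conflict** |
| Sep 2018 | Oct 2018 | Prior and concomitant (rule 2) | Concomitant only. **Conflict** |
| Sep 2018 | 3 Oct 2018 (full) | No rule applies | Concomitant. No conflict |
| 1 Sep 2018 (full) | Missing | No rule applies | Concomitant. No conflict |
| 1 Jul 2018 (full) | Sep 2018 | Prior and concomitant (rule 2) | Both. Agrees |
| Aug 2018 | 20 Aug 2018 (full) | Prior and concomitant (rule 1) | Undetermined; acceptable |

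The AE conflict before treatment thus needs four things together: a partial onset whose known part precedes Day 1, a partial end date, an end date not shown to precede Day 1, and no worsening on treatment. The medication conflict needs a known start on or after Day 1 and a partial end date.

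The calendar narrows the AE case further. If Day 1 is day d of a month, a 14-day lead-in reaches the previous month only when d − 14 ≤ 0, that is d ≤ 14 (ignoring visit windows). For a later Day 1, the onset month of a lead-in AE is the month of Day 1, so the date is truly ambiguous.

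**The case against.** The strongest reply is that the rules sit under missing-data handling and are tie-breakers, not a full algorithm. AE rule 1 does not fire for an onset month wholly within treatment, so the definition in SAP 7.7.2 must govern wherever the known date is decisive. Read that way the conflict goes away. This is probably what was meant, but the text does not say it: AE rule 2 applies to any partial onset, and a programmer coding the SAP literally would produce the conflict.

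Other objections stand and limit the point:

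- Protocol 6.2.6.1 sends AEs reported before dosing to medical history. Since dosing starts with the lead-in placebo, the exposed events are mainly lead-in AEs, with SAEs collected from consent (Protocol 6.2.6.4).
- Frequent contacts (Week -2, Days 1, 3, 6 and 7, then every two weeks from Week 3) make month-only dates for new AEs unlikely. Whether the eCRF allows partial dates cannot be seen.
- SAP 6.2 keeps these imputations out of the listings, so recorded dates remain visible there.

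A reader might also infer more than the documents support:

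- *That every patient has pre-treatment AEs at risk of miscounting, or that every AE with partial dates is miscounted.* Table 1 schedules AE review; it does not show that events occurred. The conflict needs all the conditions listed above.
- *That on-treatment drugs are moved out of the concomitant table.* They are labelled both, so that table stays right and only the prior table gains an entry.
- *That the arm comparison is biased.* The rules are the same in both arms, and SAP 7.7.2 plans no statistical comparison of AEs.
- *That counting ambiguous onsets as treatment-emergent is the error.* That is an accepted cautious convention.

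**Conclusion.** The point holds as a narrow inconsistency. Read literally, SAP 6.2 gives a classification contrary to SAP 7.7.2 for an AE whose partial onset already places it before first double-blind dose, or after last dose plus 14 days, when the end date is partial and not shown to precede first dose (and, for the pre-dose case, severity did not worsen). It gives one contrary to SAP 7.4.3 for a drug known to have started on or after Day 1 with a partial end date.

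The size is probably small but cannot be quantified, because the documents give no count or expected frequency of partial dates. The miscount should be similar in both arms, on the assumption that incomplete dates arise equally often in each. Only the descriptive TEAE and prior-medication tables are touched. The primary and secondary efficacy analyses do not use these classifications. This is a minor correction, worth making because the two sets of rules cannot both be followed.

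**What to change.** Amend SAP 6.2 so that the end-date rules apply only when the known part of the start date cannot place the start before or after first double-blind dose. Then state:

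- **AEs.** An AE with an incomplete onset is treatment-emergent if, and only if, either (a) the known part of its onset is compatible with a start between first double-blind dose and last dose plus 14 days, and it is not shown to have ended before first dose; or (b) its severity worsened on or after first dose.
- **Medications.** A drug with a known start on or after Day 1 is concomitant only.
- **Ambiguous dates.** Truly undetermined AEs stay treatment-emergent, and truly undetermined drugs stay both prior and concomitant.

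In the examples above, the July and December AEs would no longer be treatment-emergent (July unless it worsened), and the drug started on 1 Sep would be concomitant only. The AE wording also gives a result for a missing onset with a complete or missing end date, where SAP 6.2 now gives none.

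The cost is about two sentences in the SAP and a change to the derivation code, with no new data. It should be settled before unblinding, so that no judgement on safety counts is needed later.
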